8.1 Mini-Nutritional Assessment Short Version (MNA-SF) score

The MNA-SF is a validated nutritional risk screening tool that can be applied by health professionals (see [Appendix 4](#)). It was developed by Rubenstein (23), based on the MNA. Completed in less than five minutes, it can identify a decrease in food intake, an acute pathology or stress and a decrease in BMI. It also includes two questions related to the frailty of the elderly, mobility and neuropsychological problems (dementia, depression).

The MNA-SF classifies individuals as "undernourished" with a score between 0 and 7 points, "at risk for undernutrition" with a score between 8 and 11 points, and "satisfactory nutritional status" with a score between 12 and 14 points. Patients considered "undernourished" and "at risk of undernutrition" should receive a nutritional status assessment.

8.2 Bioelectrical impedanceometry

Bioelectrical impedanceometry is performed in the patient's room using the Z-Metrix impedance meter from Bioparhom. The test is performed when the patient is admitted to the ward.

The patient is positioned in dorsal decubitus, inclined at 30 degrees. The patient must rest for at least 15 minutes before the measurement. Four electrodes will be placed:

- On the flat of the back of the hand;
- At the wrist, at the level of the head of the ulna, in the intertendinous hollow;
- At the ankle, above the external malleolus;
- Above the previous electrode, spaced about 4 fingerbreadths apart.

This non-invasive test quantifies muscle, lean and fat mass as well as bone and water mass. The values are expressed in kilograms and as a percentage of body weight (see measurement procedure in [Appendix 5](#)).

The following clues will be collected:

- Muscle mass index (in kg/m^2);
- The non-fat mass index (in kg/m).²

The operator performing the bioelectrical impedanceometry will be blind to the results of other examinations performed on the patient.

The threshold used will be 7 Kg/m^2 for men and 5.7 Kg/m^2 for women, as recommended (Cederholm T et al. Clin Nutr 2019)

8.3 Muscle ultrasound

8.3.1 Operator training

Ultrasound measurements are performed by one of the investigating physiotherapists, who is not involved in the management of the patient. The physiotherapist is authorized to perform ultrasound subject to training (Avis du Conseil National de l'Ordre des Masseurs-Kinésithérapeutes (2015)). The training of the operator corresponds to the following:

- 3 days of theoretical and practical training;
- Over 100 ultrasounds supervised by an experienced practitioner.

Similarly, all the physiotherapists performing the ultrasound scans are already involved in other research projects using lung, diaphragm and peripheral

muscle ultrasound: <https://clinicaltrials.gov/ct2/show/NCT02474797>,
<https://clinicaltrials.gov/ct2/show/NCT02881814>,
<https://clinicaltrials.gov/ct2/show/NCT04373811>

and <https://clinicaltrials.gov/ct2/show/NCT04800783>.

8.3.2 Realization of the measurement

A linear probe will be used for measurements of thickness, echogenicity and cross-sectional area of the rectus femoris and vastus intermedius, according to the procedure described in **Appendix**

6. The patient is placed in the supine position (as strict as possible), with the lower limbs in extension and in a neutral position of rotation. The probe is placed on the anterior aspect of the thigh, 2/3 of the distance between the anterior superior iliac spine and the upper edge of the patella, in line with the femur.

In order to evaluate inter and intra-examiner reproducibility, the tests will be performed by two different operators and twice by the same operator, i.e. 3 identical examinations in total. In the transverse plane, the distance between the upper and lower fascia of the muscle body will be measured, directly on a frozen image. The thickness of the rectus femoris and the vastus intermedius will be measured on the right side at rest, without patient participation. The average of 3 measurements per muscle is retained to improve the reliability of the measurement.

The cross-sectional area (CSA) will also be measured. Also in the transverse plane, the cross-sectional area of the rectus femoris and the vastus intermedius will be measured using the "caliper" function to trace the limits of the muscle and measure its surface. On the same frozen image, echogenicity will be measured using the Image J software® using the entire muscle surface.

The pennation angle of the rectus femoris will also be measured in a longitudinal plane. The

SAURON
operator performing the ultrasound will be blinded to the results of the other examinations
performed on the patient.

Version 5 of 22/09/2022

9 Conduct of the research

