9.2 Inclusion visit

The inclusion visit will take place within 48 hours of the patient's or family member's consent to participate in the study. The following data will be collected:

- Age, weight, height, BMI, gender (male/female);
- Hospitalization Service;
- Reason for hospitalization;
- Background;
- Reduced food intake or absorption;
- Inflammatory situation;
- Biological markers (albumin, pre-albumin, CRP) if applicable;
- Nutritional data (weight evolution over the last months, theoretical needs, ingestas) ;
- Mini-Nutritional Assessment Short-Form (MNA-SF);
- Autonomy Score (Katz ADL);
- Ultrasound measurements;
- Bioelectrical impedance data;
- Grip force (Handgrip);
- Walking speed.

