12.1 Minimal risks and constraints added by the research

All medical and paramedical examinations and management are usually performed except for the MNA-SF questionnaire, muscle ultrasound and bioelectrical impedanceometry, which will be performed systematically in the patients included. The MNA-SF questionnaire is very quick (less than 5 minutes) and therefore causes very little inconvenience to the patient apart from an additional visit by a caregiver. Bioelectrical impedanceometry is a tool for assessing body composition using electrodes applied to the skin surface. The examination lasts an average of 15 minutes and is non-invasive and painless. The minimal constraint is related to the placement of the electrode and the duration of the examination. The ultrasound is also non-invasive and painless. The 3 ultrasounds performed will last about 30m. The minimal constraint is related to the installation of the ultrasound probe and the duration of the examination.

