16.6 Appendix 6: Protocol for performing muscle ultrasound

A linear probe will be used for the measurements. A set of predefined settings of the gain and depth parameters will be used for all measurements.

Patient positioning

The patient is installed in dorsal decubitus (as strict as possible), with the lower limbs in extension and neutral position of rotation.

Placement of the probe

The probe is placed in contact with the skin via an ultrasound gel. The pressure exerted with the probe is perpendicular to the plane of the bed, in line with the femur and must be as low as possible to obtain a representative image of the muscle. Excessive pressure will cause deformation of the subcutaneous tissues and therefore of the muscle. There are two ways of orienting the probe: in the transverse or sagittal plane.

Measurements on the quadriceps

[figure not shown]

Figure 1

The probe is placed on the anterior aspect of the thigh, 2/3 of the way from the anterior superior iliac spine to the upper edge of the patella, plumb with the femur (**Figure 1**) (39). The muscle chiefs studied were the rectus femoris and the vastus intermedius.

[figure not shown]

Figure 2

Muscle thickness

In the transverse plane, measurement of the distance between the upper and lower fascias of the muscle body (Figure 2). It is measured directly on a frozen image. The thickness of the rectus femoris (DF) and the vastus intermedius (VI) will be measured on the right. The average of 3 measurements will be taken.

[figure not shown]

Figure 3

Cross-Sectional Area (CSA):

Still in the transverse plane, measure the cross-sectional area of the rectus femoris using the caliper to delineate the boundaries of the rectus femoris (Figure 3).

Pennation angle

Place the probe along the axis of the rectus femoris muscle. The angulation of the muscle fibers in relation to the underlying fascia becomes visible (pennation of the fibers (Figure 4)). Record the image. The angle between a muscle fiber and the underlying fascia will be measured only on the rectus femoris, on the Image J software.

[figure not shown]

Figure 4

Echogenicity

Save the image used to measure the thickness and the sectional area. In the Image J software, delineate the entire muscle sectional area and analyze the variations in gray levels. The software provides a histogram with an overall gray level value ranging from 0 to 255 - 0 corresponding to black and 255 to white (28).

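### The operator who scans a patient twice is not masked from their own first thickness reading, so recall can bias the intra-examiner ICC upward

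*Combined protocol and SAP*

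**What the plan says.** Reliability and validity together form the main objective (section 3.1). Section 10.4 assesses inter- and intra-examiner reliability by intra-class correlation coefficients. The primary ultrasound variable is rectus femoris thickness (section 4.1).

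The repeat design is in section 8.3.2: "the tests will be performed by two different operators and twice by the same operator, i.e. 3 identical examinations in total". The same section says how thickness is obtained: "the distance between the upper and lower fascia of the muscle body will be measured, directly on a frozen image". Appendix 6 repeats this: "It is measured directly on a frozen image". A mean of three measurements per muscle is kept.

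On blinding, section 8.3.2 says that the "operator performing the ultrasound will be blinded to the results of the other examinations" carried out on the patient. On timing, section 9.2 lists ultrasound among the data of a single visit: "The inclusion visit will take place within 48 hours of the patient's or family member's consent to participate in the study". Section 12.1 adds: "The 3 ultrasounds performed will last about 30m".

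Appendix 6 also has the image stored for the echogenicity analysis: "Save the image used to measure the thickness and the sectional area". Echogenicity and pennation angle are then read in Image J. Thickness is not.

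**The concern.** An intra-examiner ICC measures repeatability only if the errors of the two readings are independent. Here the same person measures the same muscle twice, on screen, apparently within one visit. Someone who remembers the first value, even roughly, may place the calipers or choose the frame to agree with it. The two errors then become positively correlated, the within-patient variance shrinks, and the ICC rises with no gain in true repeatability.

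The documents do not address this. They give no order for the two operators, no minimum interval between one operator's two scans, no hiding of the first value, and no later reading of coded images for thickness. Averaging three measurements reduces random error but does not remove a pull toward a remembered value.

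At stake is the intra-examiner half of the reliability claim. Section 10.1 plans for an ICC of 0.80 against a minimum of 0.70, so a bias of a few hundredths matters. Once the data are collected, no analysis of the on-screen values can separate recall from repeatability.

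**Working it through.** **Inputs from section 10.1.** Expected ICC ρ1 = 0.80, minimum acceptable ρ0 = 0.70, k = 2 observations, α = 0.05, power 80%, N = 118.

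**Step 1: reproduce the plan's figure.** The Walter–Eliasziw–Donner approximation is N = 1 + 2(zα + zβ)²k / [(ln C)²(k − 1)], with C = (1 + kθ0)/(1 + kθ1) and θ = ρ/(1 − ρ).

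- θ0 = 0.70/0.30 = 2.333 and θ1 = 0.80/0.20 = 4.
- C = 5.667/9 = 0.6296, and (ln C)² = 0.2140.
- One-sided α: (1.645 + 0.842)² = 6.183, so N = 1 + 4 × 6.183/0.2140 = 116.6, rounded up to 117.
- The Fisher-z variant (constant 1.5 in place of 1) gives 117.05, rounded up to 118.
- Exact F-test power at N = 118 is 80.3%.
- Two-sided α gives 148.

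So 118 is reproduced with a one-sided 0.05 level. The sample size is not in question, but the formula assumes independent errors.

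**Step 2: effect of a pull toward the first reading.** The pull w is an assumption; the documents give nothing on recall. Take two unit-variance readings with true ICC ρ and let the recorded second reading be (1 − w)X2 + wX1. Then

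apparent ICC ≈ [(1 − w)ρ + w] / {[1 + (1 − w)² + w² + 2w(1 − w)ρ]/2}.

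| True ICC | w | Numerator | Denominator | Apparent ICC |
|---|---|---|---|---|
| 0.70 | 0.10 | 0.730 | 0.973 | 0.750 |
| 0.70 | 0.20 | 0.760 | 0.952 | 0.798 |
| 0.70 | 0.30 | 0.790 | 0.937 | 0.843 |
| 0.60 | 0.10 | 0.640 | 0.964 | 0.664 |
| 0.60 | 0.20 | 0.680 | 0.936 | 0.726 |
| 0.60 | 0.30 | 0.720 | 0.916 | 0.786 |

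**Step 3: a second model as a check.** Let c, also assumed, be the correlation between the operator's two measurement errors. Then apparent ICC = ρ + c(1 − ρ). For a true 0.70, c = 0.1, 0.2, 0.3 and 0.5 gives 0.73, 0.76, 0.79 and 0.85. For a true 0.65 it gives 0.685, 0.72, 0.755 and 0.825.

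**Step 4: consequence if the ICC is tested against 0.70.** Section 10.4 specifies no such test. This step uses the one implied by the sample size (one-sided 0.05, N = 118). Under the Step 3 model, the chance of concluding that the ICC exceeds 0.70 when it is exactly 0.70 is 5% with no recall. It is 16%, 40%, 71% and 99.5% at c = 0.1, 0.2, 0.3 and 0.5. For a true 0.65 it is 0.4% with no recall, then 2.5%, 11%, 35% and 95%.

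Both models point the same way. The result depends strongly on the assumed strength of recall.

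**The case against.** **Timing is inferred.** A reader might take the plan to say that the operator repeats the scan within about 30 minutes. It does not. Section 12.1 gives the total duration of the three scans, and no section says they are back to back. The second operator might already scan in between. This stands as a limit on the claim. But the order and interval are left open, so the plan as written offers no protection.

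**The blinding sentence may reach further.** Section 8.3.2 itself calls the scans examinations, so blinding to other examinations could cover the other operator's scan. That is a fair reading and would protect the inter-examiner comparison. It cannot make an operator unaware of their own earlier reading.

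**Other details are unstated.** The documents do not say that the caliper value is displayed, or whether the three averaged measurements fall within one scan. The point needs only that the scanning operator obtains the value at the bedside, which is the natural reading of measuring on the frozen image.

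**The consequence can be overstated.** A reader might infer that modest recall lifts an unacceptable ICC past a target of 0.80. The documents do not support this. In section 10.1, 0.80 is the expected value used for planning, not a success rule, and section 10.4 sets no pass mark. A 10% pull moves a true 0.60 only to 0.66, still below the minimum. Of the cases in Step 2, only a true 0.70 with 30% pull exceeds 0.80.

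**Images are saved, so a later re-read may be possible.** This helps only if the saved image carries no calipers and the re-reading is planned. Neither is stated.

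**Conclusion.** The point holds for the intra-examiner ICC of thickness. One operator reads the same patient twice with no masking of the first value, and the direction of any recall bias is upward. With an assumed pull of 10% to 30%, a true ICC of 0.70 appears as about 0.75 to 0.84, and a true 0.60 as 0.66 to 0.79. Values at or below the 0.70 minimum can therefore appear to clear it, though not at every strength of recall.

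This rests on two assumptions that the documents cannot settle: that the repeats are close enough in time for recall to operate, and how strong recall is. The plan does not show that bias will occur; it leaves the route open.

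The reach is limited. The inter-examiner ICC is affected only if the second operator learns the first operator's values or sees marks left from that scan. Diagnostic accuracy against bioimpedance is not directly affected, and N = 118 stands. Echogenicity and pennation angle are read in Image J, so recall is less immediate there. The change should be made before inclusions start, because on-screen readings cannot be corrected afterwards.

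**What to change.** In section 8.3.2 and Appendix 6:

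1. Fix the order so that the second operator's scan falls between the first operator's two scans, and state the interval.
2. Require the probe to be removed and repositioned from the anatomical landmarks at each examination.
3. Mask the first thickness value, by hiding the caliper readout if the device allows. The documents name no scanner, so this needs checking.
4. If the readout cannot be hidden, save a caliper-free image at each of the three examinations. Each operator later measures thickness in Image J on their own images, coded and in random order. A single reader should not measure both operators' images, because that would remove between-operator measurement variation and could raise the inter-examiner ICC artificially.

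Items 1 to 3 cost a few sentences of protocol text. Item 4 costs a few minutes of off-line reading per patient and a short delay before the value is available. It uses software already in the plan and needs no extra patients or visits. With off-line reading, the reliability estimate applies to that procedure and not to on-screen measurement, so the off-line values should also supply the thickness used in the accuracy analysis.

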9.1 Pre-inclusion visit

9.1.1 Verification of inclusion and non-inclusion criteria

When a patient is admitted to short stay and follow-up and rehabilitation care for diabetes-obesity, pneumology, oncology and gastro-nutrition, one of the investigators checks the presence of the inclusion criteria and the absence of the non-inclusion criteria in the institution's computerized medical record.

9.1.2 Sampling of the population

A potential of 94 patients per month eligible for this study are admitted in short stay and follow-up care and rehabilitation of diabetes-obesity, pneumology, oncology and gastro-nutrition. We anticipate a maximum inclusion of 6 patients per month for logistical reasons.

In order to obtain a representative sample of this patient population in the study, we will sample the patient population upon admission, if he/she meets the eligibility criteria and before the patient is informed and consented. The patient will be randomly assigned to either the eligible or ineligible group. Patients in the ineligible group will not be included in the study, but the number of these patients will be collected.

Patients will be sampled via a centralized random drawing system available via the internet, according to a pre-established list. This list will be programmed in advance by the study statistician. The sampling will be stratified on the care service, and unbalanced using random blocks in order to obtain a number of eligible patients of 10 per month (in order to take into account possible refusals of participation). Only the hospital's research coordinator will know the sampling list.

9.1.3 Patient information and consent

When all the criteria allow the inclusion of the patient, the investigator informs the patient of the purpose of the study during a visit to the room. The investigator provides the patient with all the information described in the information note ([Appendix 7](#)) and, if necessary, obtains the patient's free, informed and express oral consent. This consent will be recorded in the patient's computerized medical record.

The state of consciousness of certain patients (confusion, cognitive disorders) at the time of their admission will not allow them to receive information related to the research and the collection of consent and

the information will be given to the person close to the patient who has been declared a trusted person (**Appendix 8**). At any time, if the patient's neurological or cognitive state allows it, the patient will be informed of this research and his or her express oral consent will be requested for the possible continuation of the research (**Appendix 9**).

In the event of a new ban on visits to hospital wards due to the health crisis, information and oral consent from the trusted support person will be given by telephone or video conference.

9.2 Inclusion visit

The inclusion visit will take place within 48 hours of the patient's or family member's consent to participate in the study. The following data will be collected:

- Age, weight, height, BMI, gender (male/female);
- Hospitalization Service;
- Reason for hospitalization;
- Background;
- Reduced food intake or absorption;
- Inflammatory situation;
- Biological markers (albumin, pre-albumin, CRP) if applicable;
- Nutritional data (weight evolution over the last months, theoretical needs, ingestas) ;
- Mini-Nutritional Assessment Short-Form (MNA-SF);
- Autonomy Score (Katz ADL);
- Ultrasound measurements;
- Bioelectrical impedance data;
- Grip force (Handgrip);
- Walking speed.

9.3 Follow-up visit

A follow-up visit will be conducted daily to collect the patient's vital status and to verify if a discharge or transfer is planned. In the event of discharge or transfer, the following data will be collected:

- Length of hospitalization (in days);
- Vital status (death yes/no) ;
- Autonomy score (Katz ADL).

9.4 End of research visit

The end-of-research visit will take place at the patient's discharge or death. The following data will be collected:

- Length of hospitalization (in days);
- Vital status (death yes/no) ;
- Autonomy score (Katz ADL)

9.5 Summary table

	Pre-inclusion	Inclusion visit	End of research visit
Patient information and consent	✓		
Performing a pregnancy test in case of doubt	✓		
Collection of basic data (age, weight, sex, BMI, medical history)		✓	
Collection of the service and the reason for hospitalization		✓	
Associated pathologies		✓	
Biological markers		✓	
Nutritional data		✓	
MNA-SF		✓	
Ultrasound		✓	
Bio-electrical impedanceometry		✓	
Handgrip, Walking speed		✓	
Katz ADL		✓	✓
Vital status			✓
Length of hospitalization			✓

10 Statistical aspects

10.1 Calculation of the number of subjects needed

Reproducibility of ultrasound

With an expected intraclass correlation coefficient of at least $\rho_1 = 0.8$, a minimum value $\rho_0 = 0.70$ considered acceptable, a number of observations $k = 2$, a risk $\alpha = 0.05$, and a power of 80%, it is necessary to include 118 patients for the study of intra- and inter-examiner reproducibility of ultrasound (24).

Ultrasound Validity:

With an expected sensitivity and specificity of at least 90% and 85%, respectively, an estimated prevalence of muscle impairment of 45% to 60% in our hospitalized patients, for a risk $\alpha = 0.05$ and a maximum width of the confidence interval of 10%, it is necessary to include between 87 and 109 patients (25).

Therefore, it will be necessary to include 118 patients to meet the primary objective of evaluating the validity and reliability of peripheral muscle ultrasound.

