10.4 Analysis of the main objective

Inter- and intra-examiner reliability will be assessed by calculating intra-class correlation coefficients.

Validity will be assessed by calculating the areas under the ROC curve (Receiver Operating Characteristics) and calculating sensitivities, specificities, positive and negative predictive values.

The reference test for the diagnosis of impaired muscle function is bioelectrical impedance. The cut-off values used for the diagnosis of impaired muscle function are those recommended by GLIM (1): Appendicular Skeletal Muscle Index (ASMI) < 7 kg/M² in men and < 5.7 kg/m² in women.

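### The 118 patients give 80% power for one ICC tested one-sided at 5% against 0.70; section 10.4 plans no such test, and does not say whether both ICCs must pass

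*Combined protocol and SAP*

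**What the plan says.** Section 10.1 contains one reliability calculation: expected ICC at least 0.80, minimum acceptable ICC 0.70, two observations per patient, alpha 0.05, power 80%. It does not say whether alpha is one-sided or two-sided. It concludes that "it is necessary to include 118 patients for the study of intra- and inter-examiner reproducibility of ultrasound", and then that "it will be necessary to include 118 patients to meet the primary objective of evaluating the validity and reliability of peripheral muscle ultrasound".

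Section 8.3.2 sets out the scans: "the tests will be performed by two different operators and twice by the same operator, i.e. 3 identical examinations in total". The intra-examiner pair and the inter-examiner pair therefore have at least one operator in common.

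Section 10.4 gives the whole planned reliability analysis: "Inter- and intra-examiner reliability will be assessed by calculating intra-class correlation coefficients". It names no minimum value, test or decision rule. The 0.70 appears only in section 10.1. Section 10.2 adds, for the study as a whole, a 5% significance level and a 95% confidence interval for every estimate, and ties neither to 0.70.

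**The concern.** Reliability is half of the main objective (section 3.1), and it sets the sample size, because the validity calculation asks for fewer patients (87 to 109). The 118 was derived from a hypothesis test that the analysis section does not carry out, and one calculation was applied to two coefficients.

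Three things are therefore left open: whether the stated 80% refers to each ICC or to both, what level the comparison with 0.70 uses, and what counts as success. The answers change the conclusion. At 118 patients, the test behind the sample size passes if the observed ICC is about 0.77 or more; a two-sided 95% interval read against 0.70 needs about 0.78. If these choices are made after the data are seen, the same result can be reported as acceptable or as not shown.

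**Working it through.** **Inputs.** From section 10.1: ρ0 = 0.70, ρ1 = 0.80, k = 2, α = 0.05, power 80%, n = 118. From section 8.3.2: three examinations per patient, two by operator A (A1, A2) and one by operator B. From section 10.2: 95% intervals.

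**Step 1: the plan's own figure.** The usual sample size formula for an ICC is n = 1 + 2k(z_α + z_β)² / [(k − 1)(ln C)²], with C = [1 + kρ0/(1 − ρ0)] / [1 + kρ1/(1 − ρ1)].

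- C = (1 + 2 × 0.70/0.30) / (1 + 2 × 0.80/0.20) = 5.667/9 = 0.6296, and (ln C)² = 0.2140.
- One-sided: (1.645 + 0.842)² = 6.183, so n = 1 + 4 × 6.183/0.2140 = 116.6, that is 117. This is one patient from the stated 118.
- Two-sided: (1.960 + 0.842)² = 7.849, so n = 147.7, that is 148.
- With k = 3: 80 one-sided, 101 two-sided.

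Of these, only the one-sided calculation for one ICC with two observations fits 118.

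**Step 2: exact power for one ICC at 118.** The one-way F test rejects when the observed F ratio exceeds 5.667 × F(1 − α; 117, 118). Power is P(F > C × F(1 − α; 117, 118)), and an F ratio corresponds to an ICC of (F − 1)/(F + 1).

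| Level | F quantile | Observed ICC needed | Power at true ICC 0.80 |
|---|---|---|---|
| One-sided 5% | 1.356 | 0.770 | 80.3% |
| One-sided 2.5% (lower limit of a two-sided 95% interval) | 1.438 | 0.781 | 70.4% |

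**Step 3: both ICCs at 118.** This was simulated. Each patient has readings A1, A2 and B with total variance 1: between-patient variance equal to the inter-examiner ICC, patient-by-operator variance equal to the intra-examiner minus the inter-examiner ICC, and the remainder as error. The intra-examiner ICC uses A1 and A2; the inter-examiner ICC uses A1 and B. Runs: 100,000 for the rows with both ICCs at 0.80, 40,000 for the others.

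| True intra / inter ICC | Level | Both exceed 0.70 |
|---|---|---|
| 0.80 / 0.80 | one-sided 5% | 70.1% |
| 0.82 / 0.80 | one-sided 5% | 77.8% |
| 0.85 / 0.80 | one-sided 5% | 80.1% |
| 0.90 / 0.80 | one-sided 5% | 80.6% |
| 0.80 / 0.80 | one-sided 2.5% | 57.2% |

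With both ICCs at 0.80, the two log F ratios have a correlation of about 0.54, because the pairs share a scan. Without that sharing, joint power at one-sided 5% would be 64.4%.

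**Step 4: size for joint power.** With both ICCs at exactly 0.80 and one-sided 5%, joint power is 79.2% at 145 patients and 80.6% at 150.

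**The case against.** The strongest reply is that nothing in section 10.1 is miscalculated. The 118 reproduces, and 80% for each coefficient is a tenable reading. That stands: this is not an arithmetic error.

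A reader might infer that the study simply has 70% power for reliability. The documents do not support that without conditions. No section says that both ICCs must pass, and section 10.1 plans for an ICC of at least 0.80, so 70% is the value at the lowest planned ICC for both. Disagreement between operators affects only the inter-examiner pair, so the intra-examiner ICC may well be the higher; at 0.85 the joint power is back to about 80%.

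A reader might also infer that the point estimate will be set against 0.70, which would give about an even chance of passing when the true ICC is exactly 0.70. No section plans that comparison, and section 10.2 promises an interval for each estimate. The error rate of such a rule cannot be charged to this plan.

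The promise of intervals does not close the gap, however. Section 10.2 links them to no threshold. If they are two-sided and are read against 0.70, they apply a stricter level than the one behind 118, and the stated 80% is not reached even for one ICC.

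**Conclusion.** The point holds as a mismatch between the sample size and the analysis, in a co-primary part of the objective. The stated 80% is the power of one ICC under a one-sided 5% test that section 10.4 does not contain. Under the only interval planned, read as two-sided against 0.70, power is about 70% for each ICC and 57% for both when both are 0.80. If both must pass at one-sided 5%, joint power lies between about 70% (both exactly 0.80) and about 80% (intra-examiner 0.85 or more, inter-examiner 0.80).

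These figures rest on four assumptions: the one-sided level, inferred because only it reproduces 118; a one-way ICC with normal errors; a shared A1 scan; and, for the joint figures, a rule that both must pass, which the plan neither states nor excludes. The study is not invalidated, but the rule should be fixed before analysis.

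**What to change.** Make two changes and keep 118.

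1. In section 10.1, replace the general power statement with: *80% power for each ICC separately (one-sided 5%); about 70% that both succeed if both are exactly 0.80, about 80% if the intra-examiner ICC is 0.85 or more* (with the inter-examiner ICC at 0.80).
2. In section 10.4, add: *Each ICC of rectus femoris thickness is judged acceptable if its one-sided 95% lower confidence limit (the lower limit of the two-sided 90% interval) exceeds 0.70. Ultrasound is concluded reliable only if both the intra- and the inter-examiner ICC meet this.*

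The rule uses the plan's own minimum, its own 5% and the measurement that section 4.1 names as primary. The two-sided 95% intervals of section 10.2 can still be reported for description. There are no extra patients, visits or scans. The cost is a few sentences and a less favourable stated power. If the sponsor wants 80% joint power with both ICCs at exactly 0.80, that would take about 150 patients; the fix does not require it.
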